1 PROTOCOL SUMMARY

1.1 SYNOPSIS

Title:	Increasing African Immigrants' Breast Cancer Screening
Grant Number:	R21MN012863
Study Description:	The barriers and facilitators to breast cancer screening for other minority groups from underserved populations, such as African Americans and Latina women have been studied. Less is known about these for African immigrant women and how to most effectively engage their participation in regular screening. The long term goal of the proposed project is to conduct a clinical trial that tests the feasibility of an adapted intervention to increase breast cancer screening rates for African-born immigrants. The study team plans to pursue the following specific aims: (1) Identify barriers and facilitators to breast cancer screening among African-born immigrants and (2) Culturally adapt and pilot test the Witness Project breast cancer education program for African-born women.
Objectives * :	Primary Objective: Adapt and pilot the Witness Project breast cancer education program. Secondary Objectives: Identify barriers and facilitators of breast cancer screening
Endpoints * :	Primary Endpoint: change from baseline assessment of mammogram screening intention and mammogram location and appointment. Secondary Endpoints: change from baseline assessment of perceived breast cancer risk and self-efficacy for mammography.
Study Population:	Men or women 18 and older; stakeholder or leader in African immigrant community; English or French speaking (Aim 1) African-born women 40 years and older; English or French speaking (Aim 1) African-born women 38 years and older; English or French speaking (Aim 2)
Phase * or Stage:	Not Applicable
Description of Sites/Facilities	Participants will be enrolled at one site (Icahn School of Medicine at Mount Sinai) in collaboration with African immigrant-serving community organizations.
Enrolling Participants:	
Description of Study	
Intervention/Experimental	African immigrant women are at significant risk for not participating in preventive screening, such as for breast cancer. Thus, this project will culturally adapt an existing evidenced-based intervention, the Witness Project, by identifying barriers and facilitators to screening for African-born women and, guided by the Health Belief Model, incorporate those findings into a group-based narrative education program for English and French-speaking African immigrant women. The program content will include: (1) information about the benefits of early detection of breast cancer screening, (2) education about disparities in breast cancer, (3) education about disparities in breast cancer screening among African immigrant women, and (4) will address the unique barriers and facilitators of African immigrant women identified in Aim 1 of this study.
Manipulation:	
Study Duration * :	18 months
Participant Duration:	60 min (Aim1); 90 mins (Aim 2)

1.2 SCHEMA

Pre-Intervention Assessment

- Pre-screen potential participants by inclusion and exclusion criteria;
- Schedule in-depth interview or survey

[figure not shown]

Based on "NIH Protocol Template for Behavioral and Social Sciences Research"

4

Effective Date: 1/26/2024

End Date: 1/25/2025

Based on "NIH Protocol Template for Behavioral and Social Sciences Research"

1.3 SCHEDULE OF ACTIVITIES

	Pre-consent	Time 1
AIM 1		
Review Eligibility	X	
Schedule in-depth interview or survey	X	
Informed Consent		X
Demographics		X
In-Depth Interview/Survey		X
Data Analysis		
AIM 2		
Cultural adaptation of the Witness Project cancer education program for African-born immigrant women	X	N/A
Pre-screening of potential participants by inclusion and exclusion criteria	X	N/A
Informed Consent	N/A	X
Pre-Intervention assessments	N/A	X
Administration of the adapted version of the Witness Project	N/A	X
Post-Intervention assessments	N/A	X
Outcome Evaluation		

Based on "NIH Protocol Template for Behavioral and Social Sciences Research"

2 INTRODUCTION

2.1 STUDY RATIONALE

New York City (NYC) is home to a large and diverse immigrant population. Specifically, African immigration has increased over 750% in the past 20 years with a high concentration living in NYC.^{1,2} African immigrants are a very heterogeneous population with no individual country accounting for more than 14% of the total; most are likely to live below the poverty line, less likely to have health insurance, more likely to have low health literacy, and less likely to visit a doctor particularly for primary/preventive care.^{3,4,5} While overall screening rates for breast cancer have increased significantly in NYC in the last decade^{6,7}, many immigrant groups still face significant barriers to preventive health care, including lack of insurance, poor health care access and language difficulties. Without access to primary care, many preventive services, like breast cancer screening, go unattended. For example, annual mammography exams and timely follow-ups after abnormal findings are crucial for the early detection of breast cancer, which has been shown to be one of the most important factors of increased survival.

Health disparities plague the health care system and arise from a complex interplay of economic, social and cultural factors. The Health Belief Model (HBM) provides a framework for addressing cultural health disparities related to preventive health care and cancer screening by positing that making a decision to engage in a health behavior (e.g., cancer screening) is determined by weighing perceived threats (susceptibility, barriers) versus benefits.¹¹ Traditionally, health information has been presented in didactic forms (i.e., statistical evidence/facts) to educate, persuade, and engage target communities.^{12,13} Narrative communication (i.e., storytelling, personal testimonials) has emerged as a method for supporting and motivating behavioral change including personal experiences with cancer or screening. The appeal and success of narrative communication stem from its familiarity as a basic mode of human interaction.^{14,15} Our own work in minority and immigrant communities has shown that narrative communication can increase participation in cancer screening. Thus group-based narrative educational programs could play a significant role in promoting healthy preventive engagement including breast cancer screening among African immigrants.^{16,17,18,19}

The proposed project is innovative in several important ways. First, to our knowledge, this study is the first to examine barriers and facilitators regarding the uptake of breast cancer screenings among eligible African-born women immigrants in NYC. A community-based intervention is one that entails a strategy for education and behavior change by increasing awareness and knowledge through public service announcements, education, written manuals, etc. Research on breast and cervical cancer screenings has targeted African Americans and Latinas^{20,4,21,22,23}; but few have targeted African-born populations. Second, a community-based recruitment strategy for the cancer screening education intervention is proposed. Adopting this approach will allow us to reach African-born immigrant women at places they frequent and provide new information about the barriers and facilitators to breast cancer screenings, particularly among those who are currently unable to access health care. Third, to our knowledge, this is the first study to obtain the perspectives of African-born community leaders about how African immigrant women's participation in breast cancer screening can be improved. Fourth, this project will represent the first approach to pilot test the feasibility and acceptability of a narrative approach in educating African-born immigrants about breast cancer screening. While education programs can improve cancer and

Based on "NIH Protocol Template for Behavioral and Social Sciences Research"

cancer screening knowledge^{20,24} and increase intent to get screened for other underserved populations, it remains to be seen if a theory-informed and evidence-based education program can be similarly effective among African-born immigrants. By incorporating an understanding of the barriers and facilitators to breast cancer screenings, we will target important facilitators and potential barriers to address in future interventions.

The long term goal of the proposed project is to conduct a randomized clinical trial that tests the adapted intervention to increase breast cancer screening rates for African-born immigrants. In the short term, we plan to pursue the following specific aims: (1) Identify barriers and facilitators to breast cancer screening among African-born immigrants and (2) Culturally adapt and pilot test the Witness Project breast cancer education program for African-born women. Thus, we will culturally adapt an effective, innovative intervention to address this significant health disparity in African-born immigrant communities. Once we have pilot tested the feasibility and acceptability of the intervention, we will apply for R01 funding.

2.2 BACKGROUND

Minimal research has been conducted specifically on the needs of African immigrant groups. Though African immigrants and African Americans/blacks share a common ancestral history, they are distinct cultural groups with differing values, perceptions, experiences and languages.⁸ Available research studies often erroneously classify each culture as one homogenous group (i.e., African American/Black), which limits our understanding of the specific needs of African immigrants. Most research on the cancer control needs of African immigrants has focused on individuals from Nigeria, Somalia and Ghana⁹, furthering limiting our understanding of individuals who are not from these countries. Immigrants from Africa come from many different countries that have distinct languages.¹⁰ Lack of knowledge of the US healthcare system is a persistent problem for African immigrants and addressing language access and health literacy may be one approach to improving healthcare engagement in this population.

Our breast cancer screening data in this population of African-born immigrants, when corrected for age, shows that only 56% have ever had a mammography for breast cancer screening. *This finding demonstrates the need for breast cancer screening awareness and education within this population.* We have conducted robust culturally targeted outreach into several minority communities. The Witness Project (WP) is a community-based cervical and breast cancer education program that is designed to meet educational and cultural levels of underserved African American women. The WP model is a belief and theory-based intervention incorporating the Health Belief Model, locus of control beliefs, social learning theory, transtheoretical model of change and the 4MAT System.⁴³ The program begins with a narrative presentation by a breast cancer survivor who briefly shares her personal experience of breast cancer, from diagnosis to treatment and survivorship. Lay volunteers present educational information about breast cancer risks and protective factors, demonstrate how to perform a breast self-examination and a question and answer session concludes the program. Research by [name] (Co-I) and [name] successfully replicated the Witness Project in 22 states at 40 unique sites including NYC. Replication was achieved using an Implementation Guide, locally produced, award winning video (now on CancerControl PLANET RTIPs) and training curriculum developed by [name] and [name] (National Cancer Institute Cancer Control Planet). In NYC, we conducted hundreds of programs at a variety of community sites and have educated over 3,000

participants.^{44,20,45,12} *This research demonstrates our ability to reach culturally targeted members in the community and over 15 years of community-based research experience.*

Development of *Esperanza y Vida*: A unique aspect of the Witness Project is the ability to adapt the program to another culture as evidenced by *Esperanza y Vida* (EyV). In 2003, [name] and colleagues initiated EyV to expand this breast educational program among Hispanic populations in a culturally and linguistically congruent, community-based approach.^{4,12} EyV development was conducted with members of the target group, including qualitative studies, to ensure the adaptation would be culturally appropriate and meaningful.^{46,47} The social network characteristics and language preferences (Spanish) assessed and integrated into the intervention to include such factors of where to present the programs (e.g. both community and faith-based locations) and the need to educate men about issues related to women's health.^{22,4} *This successful replication and adaptation demonstrates our ability to adapt education programs through vigorous qualitative methods and pilot testing as well as to address linguistic needs of different cultural groups.*

2.3 RISK/BENEFIT ASSESSMENT

2.3.1 KNOWN POTENTIAL RISKS

Physical risks in this study are minimal. The surveys include questions that are not different from those that might be asked or presented by a health care provider and thus do not pose greater than minimal risk. Although the chances of psychological distress are minimal, any psychological distress will be monitored by the staff and reported to the Principal Investigator.

2.3.2 KNOWN POTENTIAL BENEFITS

Although we cannot guarantee that participants may benefit directly from study participation, prior study participants have reported that they enjoyed providing researchers with greater knowledge of their experience in hopes of aiding the design of cancer prevention programs and materials and in possibly benefiting others. It is possible that for patients, participating may raise awareness of their need to uptake cancer screening and their decision to undergo screening. There are minimal physical risks posed by this study. Risk of psychological distress is possible as a reaction to some study questions about cancer. Research staff will monitor participants' reactions. Through the ongoing monitoring process of the study (e.g., regular meetings with research staff), the PI will be informed of any concerns/distress that occur at any point in the study. Given the potential gains to participants, the ratio of risk to benefits is quite low and reasonable.

2.3.3 ASSESSMENT OF POTENTIAL RISKS AND BENEFITS

The knowledge gained by conducting this research will help us to potentially develop interventions to increase the uptake of breast cancer screening among African-born immigrant women at high risk for breast cancer. There is minimal physical risk and minimal risk of psychological distress as a reaction to some study questions about cancer and screening; however these risks are overpowered by the

potentially life-saving benefits of cancer screening to prevent the onset of breast cancer in African born immigrant women.

Given the potential gains to participants, the ratio of risk to benefits is quite low and reasonable. There are no effective alternative procedures for collecting these data

3 OBJECTIVES AND ENDPOINTS

OBJECTIVES	ENDPOINTS	JUSTIFICATION FOR ENDPOINTS
Primary		
Adapt and pilot the Witness Project breast cancer education program	
Primary Outcome Measure:
 
1. Mammogram intention: Participants' intentions to complete breast cancer screening by responding to:
 
A. For women who had a mammogram in the past: Do you think you will have another one? Yes, later this year (2023) Yes, next year (2024) Yes, in two years (2025) No Not sure/don't know
 
B. For women who never had a mammogram in the past: Do you think you will have one? Yes, later this year (2023) Yes, next year (2024) Yes, in two years (2025) No Not sure/don't know
 
2. Mammogram location and appointment: Do you know where you could go to get a mammogram? Yes No Not sure
 
Secondary Outcome Measures:
 
3. Perceived Risk: Participants' perceived risk of developing breast cancer: What do you think are the chances that you will have breast cancer at some point in your life? (1. Very low 2. Somewhat low 3. Moderate
	
Intention to screen is hypothesized to be a dependent variable.
 
Perceived risk is hypothesized to be mediator variable that could explain the causal mechanisms of the intervention.

OBJECTIVES	ENDPOINTS	JUSTIFICATION FOR ENDPOINTS
	
4. Somewhat high 5. Very high) [Time Frame: Immediate]
 
4. Comparison Perceived Risk: Participants' perceived risk of developing breast cancer: Compared to the average person your age and gender, would you say that you are (1. Less likely to get breast cancer 2. About as likely to get breast cancer 3. More likely) to get breast cancer [Time Frame: Immediate]
 
5. Self-Efficacy for Mammography: Ten items will be used to examine participants' self-efficacy for undergoing mammography using a 5-point Likert-type scale. (Full scale from 1 to 5, with higher score indicating greater self-efficacy) [Time Frame: Immediate]
	Self efficacy is hypothesized to be a mediator variable that could explain the causal mechanisms of the intervention.
Secondary		
Identify barriers and facilitators of breast cancer screening	N/A - survey/interview completion	N/A
Tertiary/Exploratory		
N/A	N/A	N/A

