session and f) completion of the post-program survey including feasibility questionnaire and feedback discussion. After the completion of the question and answer session, participants will be given breast cancer resource guides with local information about how and where to obtain screening. The program will take approximately 90 minutes to complete. Participants will receive an incentive (\$60 gift card) for their participation. Participants will complete a pre-program survey and a post-program survey to assess changes in HBM constructs. The post-program survey will also include a feasibility questionnaire.^{62,63,64,65} The programs will be evaluated using a program summary template that [name] and colleagues have used in previous studies. The summary collects information about the length of the program, number of participants attending the program, gender of program participants, location and site of the program, number of staff and volunteers present, and type of site (faith-based or community-based).

For both in person and virtual educational programs, demographic and pre-post surveys will be primarily collected via RedCap. For virtual programs, participants will be provided with RedCap survey links via chat. For in person programs, participants will be able to complete surveys through RedCap on their own devices or on devices provided by the study team. Hard copies of the surveys will also be available for completion for in person educational programs. All pre and post assessments, collected via RedCap or hard copy of surveys, will be linked only via participant study ID. Assessments will not collect any PHI. They will be anonymous as participant names will not be collected.

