9.4 STATISTICAL ANALYSES

9.4.1 GENERAL APPROACH

For Aim 1 demographic characteristics of the participants will be reported. Data from the quantitative surveys will be analyzed to identify predictors of non-adherence to breast cancer screening. We will conduct univariate and bivariate analyses of the data to provide descriptive summaries of the data, including demographics and responses to primary outcome measures. Data from the audio-recorded in-depth interviews will be transcribed verbatim from audio recordings (using a transcription service). Analyses of the qualitative data will be conducted using the PEN-3 model, which is a method of analyzing data focusing on social processes and actions. The goal of our qualitative research is to identify the unique barriers and facilitators African immigrant women encounter with breast cancer screening. In line with this approach, the coding steps of open coding, axial coding, and selective coding will be used to identify categories and develop properties. Memoing will be conducted throughout the process. A constant comparative method will be used to generate theoretical categories and refine concepts.

For Aim 2, we will conduct univariate and bivariate analyses of the data to provide descriptive summaries of the data, including demographics and responses to primary outcome measures. Independent samples t tests will be used to compare changes in the primary outcomes measures pre-education and post-education. Using a pre-post test design, we will analyze differences in the three primary outcomes: screening intentions, self-efficacy and perceived risk immediately before viewing the educational program and immediately after viewing the program.

To determine program efficacy and sample size estimates for a future intervention, a generalized linear modelling approach will be used with logistic regression. We will use a repeated measures ANOVA to analyze differences in the primary outcomes: screening intentions and HBM constructs (e.g., self-efficacy and perceived risk) immediately before viewing the educational program and immediately after viewing the program. We will conduct univariate and bivariate analyses of the data to provide descriptive summaries of the data, including demographics and responses to primary outcome measures.

Based on "NIH Protocol Template for Behavioral and Social Sciences Research"

23

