	
3) The length of the Aim 2 intervention increased from 60 to 90 minutes.
 
4) Aim 2 compensation increased to \$60.
 
5) The measures for primary endpoints have been refined.
 
6) Mention of research information material for Aim 2 was included.
 
7) Approach to qualitative data analysis was updated.
	
sound to include women under 40. This is also based on the request a few participants have made about the inclusion of younger women in the educational program.
 
2) Our primary endpoint is intention to have a screening mammogram within 2 years, so it is sound to include women who have been screened recently.
 
3) We have also increased the length of the intervention from 60 to 90 minutes to account for the assessments that participants will complete for research purposes.
 
4) Since the time of the intervention increased, the compensation amount has also increased in order to accurately reflect their time and effort.
 
5) Primary Endpoint: change from baseline assessment of mammogram screening intention and mammogram location and appointment. Secondary Endpoints: change from baseline assessment of perceived breast cancer risk and self-efficacy for mammography.
 
6) Aim 2. We have requested a waiver of written consent due to the extremely low risk of this research as no PHI will be collected from participants. We are unable to consent participants prior to the program because we will not have their contact information (as we are not collecting any PHI) – participants will be recruited and invited to the programs by community partners. We anticipate having up to 10 participants in each program and we will have limited staff available to consent participants. On the day of the program, participants will

--	---	--

		review, either via RedCap or in person with a hard copy, the Research Information Sheet that will provide details about the research study. If individuals agree to participate in the study, they will confirm their eligibility for the study. 7) The study team decided to adopt a different, leaner approach to coding.

Based on "NIH Protocol Template for Behavioral and Social Sciences Research"

34

Effective Date: 1/26/2024

End Date: 1/25/2025

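### The primary mammogram-intention item prints the years 2023, 2024 and 2025, which contradict their own labels in any survey given as written during the document's stamped period (26 January 2024 to 25 January 2025)

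*Combined protocol and SAP*

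**What the plan says.** The synopsis (section 1.1) gives the "Primary Endpoint: change from baseline assessment of mammogram screening intention and mammogram location and appointment". It sets no time window.

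Section 3 gives the item in two versions: A for women who have had a mammogram and B for women who have not. Both offer the same three Yes answers, "Yes, later this year (2023) Yes, next year (2024) Yes, in two years (2025"), followed by No and an unsure option. Each Yes answer therefore carries both a relative label and a fixed calendar year.

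The page footers, for example in sections 1.2 and 10.4, carry the stamps "Effective Date: 1/26/2024" and "End Date: 1/25/2025". The last logged change to this measure is version 1.3 of 9 March 2023 (section 10.4): "The measures for primary endpoints have been refined". The rationale for that version describes the primary endpoint as intention to be screened within two years. The horizon is stated only there.

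On analysis, section 9.4.1 says "Independent samples t tests will be used to compare changes in the primary outcomes measures pre-education and post-education" and "We will use a repeated measures ANOVA to analyze differences in the primary outcomes: screening intentions and HBM constructs". It also names logistic regression. No section says how the five answers are coded, or whether label or year governs.

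Aim 2 surveys are completed mainly in RedCap, in person or virtually. Section 6.1.1 adds: "Hard copies of the surveys will also be available for completion for in person educational programs".

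**The concern.** An answer option that names a time in two ways works only while the two ways agree. These agree in 2023. A document in force from late January 2024 still carries them, with no instruction to replace the years and no sign that they are examples.

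Two things are at stake. First, two women with the same plan can tick different Yes options, one going by the label and the other by the year, so the timing of a Yes cannot be recovered from the data. Second, a plan that a label covers but no printed year covers may be ticked as No or Not sure. That error crosses the line between intending and not intending, so collapsing the answers to Yes against the rest does not fully remove it.

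Women answer on a form, and section 2.1 describes the population as more likely to have low health literacy. No section describes a step at which staff explain which part of the option to follow.

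**Working it through.** The plan gives no calculated figure on this point. The margin of error of ±12% in section 9.2 does not depend on the item's wording. The check is calendar arithmetic.

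**Inputs.** Printed years 2023, 2024, 2025 (section 3). Stamped period 26 January 2024 to 25 January 2025 (footers). Aim 2 sample of 64 (sections 5.1 and 9.2). Eight programs (section 6.1.2).

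**Step 1: label against printed year.** Year meant = survey year + 0, 1 or 2. Offset = printed year − year meant.

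| Survey given in | Years meant by the labels | Years printed | Offset | Options that agree | Meant years with no printed match |
|---|---|---|---|---|---|
| 2023 | 2023, 2024, 2025 | 2023, 2024, 2025 | 0 | 3 of 3 | none |
| 2024 | 2024, 2025, 2026 | 2023, 2024, 2025 | −1 | 0 of 3 | 2026 |
| January 2025 | 2025, 2026, 2027 | 2023, 2024, 2025 | −2 | 0 of 3 | 2026, 2027 |

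**Step 2: how much of the stamped period is affected.** 26 January to 31 December 2024 is 366 − 25 = 341 days. 1 to 25 January 2025 is 25 days. The total is 341 + 25 = 366 days, and no option agrees with itself on any of them. The first option names a past year throughout.

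**Step 3: what one plan can turn into.** Options are numbered 1 to 3 in printed order.

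| Session | Planned year | Option by label | Option by year |
|---|---|---|---|
| 2024 | 2024 | 1 | 2 |
| 2024 | 2025 | 2 | 3 |
| 2024 | 2026 | 3 | none (No or Not sure possible) |
| January 2025 | 2025 | 1 | 3 |
| January 2025 | 2026 | 2 | none (No or Not sure possible) |

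A 2026 plan stated in 2024 lies within the two-year horizon of section 10.4 if years are counted as the labels count them.

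**Step 4: possible exposure.** The documents do not date the sessions. Assuming equal sessions of 64 / 8 = 8 women, 0, 1, 4 or 8 sessions held after 2023 with the printed wording would affect 0, 8, 32 or 64 women. This is the whole possible range, not an estimate.

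**The case against.** The strongest reply is that no exposure has been shown. The stamp dates the document, not the sessions. The years fit version 1.3 of March 2023 exactly, and sessions held in 2023 would have used a correct item. The form may also have been updated in RedCap. All of this stands: the number of women affected may be zero. It does not settle the point, because the document in force for 2024 instructs otherwise and records no update.

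A second reply is that timing may never be analysed. The plan states no timing score, a 0/1 intention variable would serve the t tests and ANOVA, and logistic regression is named as well. With a two-year horizon, all three labels count as intending. This also stands in part. A reader might infer that a timing score is distorted by a definite amount, but no such score is in the plan, so no amount can be given. The reply does not cover the woman whose plan has a label but no printed year and who may answer No or Not sure.

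A third reply is that both surveys are given in one session with the same wording. A reader might infer that the mismatch manufactures an intervention effect. The documents do not support that: a woman who reads the item the same way twice shows no false change. A false change would need her to switch between label and year from one survey to the next. That is possible, but nothing in the documents shows that it happens.

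Feasibility is judged by a separate 80% criterion (sections 9.1 and 9.3), whose listed parameters do not include this item.

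**Conclusion.** The point holds conditionally. In any Aim 2 survey given as written during the stamped period, none of the three Yes options agrees with itself: each printed year is one year early in 2024 and two years early in January 2025. Timing among the Yes answers is then ambiguous, and a plan after 2025 that a label still covers can be recorded as No or Not sure.

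The conclusion rests on two assumptions: that some sessions took place after 2023, and that the form matched section 3. The documents confirm neither, so exposure lies anywhere from 0 to 64 women. Surveys given in 2023 are unaffected.

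The documents do not support reading this as an invalid primary endpoint or a biased pre-post comparison. It is a real contradiction in a primary measure, of unknown reach, and it should be corrected because doing so costs little.

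**What to change.** - **Wording.** For every session after 2023, delete the printed years or fill them from the survey date (2024, 2025, 2026 in 2024; 2025, 2026, 2027 in January 2025). Do this in versions A and B, in English and French, in RedCap and on hard copies, and amend section 3 to match. If the form in use already differs, record that instead.
- **Surveys already given.** Use the session date to identify any printed-year surveys given after 2023. The program summary in section 6.1.1 lists no date, but the coordinator schedules each program, so dates should be traceable. Record them from now on.
- **Analysis.** Do not interpret timing among the Yes answers of those surveys. Repeat the pre-post intention analysis without them as a sensitivity check.

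The cost is a small wording change with IRB notification and one extra analysis. The check loses precision as more women are excluded, and it cannot be run if all 64 are affected. In that case the limitation has to be reported.
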